CT images are first resliced to match the resolution and location of PET images. As performed in previous studies 2, a supraclavicular ROI is first manually drawn on the CT images. Within that area, the fat ROI is segmented using the CT images and an intensity window from -200 to -50 HU. Subsequently the fat ROI is segmented into WAT and BAT ROIs by using the ¹¹C-MRB PET images: Standardized Uptake Value (SUV) ≥ 1.25 for BAT, SUV < 1.25 for WAT.

Brain ROIs for predetermined NET-rich areas of the brain, including the locus ceruleus, raphe, thalamus and hypothalamus were defined in template space and are applied to the PET images by using the participant's MR image as an intermediate step. For analysis of tracer uptake, mean SUV will be reported for segmentation of adipose tissue. Because the distribution volume ratio (DVR) is a more precise measurement of uptake for reversible tracers ³ such as ¹¹C-MRB, regional quantification of ¹¹C-MRB uptake as DVR (V_T / V_{ND}), estimated via multilinear reference tissue model 2 (MRTM2) ^{4,5} ($t^* = 30$ min) using the occipital cortex, a region with low NET density ^{2,5,6} as the reference region. MRTM2 reduces the variability of MRTM (4) parameter estimates by fixing one of the three parameters, the parameter k_2' , which is only related to the reference region time-activity curve, to a common value for all target regions. In this study, the parameter k_2' was fixed to 0.021 min⁻¹, based on previous brain studies and previous BAT PET studies ². In addition to DVR, MRTM2 can estimate R_1 , the relative radioligand delivery, using a 1 tissue compartment model (1TC). For the 1TC model, volume of distribution, $V_T = K_1/k_2$, where K_1 (mL/min⁻¹/mL⁻¹) is the rate constant of radiotracer from plasma to tissue of target organ and k_2 is the rate constant from tissue to plasma. Using a reference region with non-displaceable binding (e.g. occipital lobe) we can estimate similar rate constants: $V_{ND} = K'_1/k'_2$. Recalling that K_1 and K'_1 are the rate constants for transfer from plasma to the tissue and reference region, respectively, then we can estimate relative radioligand delivery as $R_1 = K_1/K'_1$.

The maximum number of attempts for each failed/incomplete imaging and test is 2 times.

Visit 3 – Whole body PET Imaging Visit - High-Carbohydrate Mixed Meal Test (MMT)

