Muscle sympathetic nerve activity (MSNA): Microneurography is the gold standard, most sensitive and reliable MSNA assessment in humans. The primary measure of sympathetic nervous system activity is peripheral nerve activity, as measured by MSNA.

Muscle sympathetic nerve activity will be quantified by identification and measurement of sympathetic bursts in the integrated neurogram and expressed as burst frequency (number of bursts per unit time). ECG surface electrodes are applied to the chest, an elastic band incorporating a strain gauge element is strapped around the thorax for recording respiratory movements, and a sensor cuff of a servopulse-plethysmography arterial pressure monitor (FINAPRES, Ohmeda) is placed on the middle phalanx of the long finger (held at heart level). The experiments are carried out in an environmentally controlled chamber at an ambient temperature of 27.0 ± 0.1 °C. The experiment will begin with a 60-minute control period. During such time the subjects rest in the reclined position.

Measurements of HR, BP, and EKG (beat-to-beat) will also be obtained during the procedure. An intravenous catheter will be inserted into a forearm vein for blood sampling. Following the instrumentation period, resting HR, pulse interval (PI), BP, and MSNA will be recorded for 10 minutes. Following these measurements, plasma will be taken for measurements of insulin, glucose, free fatty acids, norepinephrine, and epinephrine levels. Approximately 20 mL of blood will be drawn at this visit. After the first blood sample and the 10-min rest phase, subjects will begin a seven-minute period of rest with paced breathing (12 breaths per minute) while HR, BP, PI and MSNA are measured. The subjects will synchronize breathing to a metronome set to a cadence of ~12 breaths per minute (0.2 Hz).

Procedure: Microneurography Recording of multiunit postganglionic muscle sympathetic nerve activity (MSNA) will be made from the common peroneal nerve as it winds around the fibular head with the subject in the supine position with the subject's thigh comfortably

HIC 2000030749

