supported. This procedure requires us to first trace the course of the nerve using small electrical stimuli applied to the surface of the skin over the nerve or use the ultrasound to visually assist. This allows the microneurographer to find and focus the recording electrode tip on a nerve fascicle associated with muscle sympathetic activity. The time required to focus the electrode on the nerve averages about 30 min and will not exceed 60 min. In optimal conditions the track of the nerve from superficial stimulation is accurate and the nerve remains in position during insertion. An uninsulated subcutaneous electrode will serve as the reference. Mechanoreceptor afferent activity can be recorded during light tapping on the muscle belly or passive muscle stretch. A suitable intrafascicular recording site for MSNA consists of regular bursts and synchronous with the cardiac cycle. The neural activity is amplified (2x104), filtered (0.5-5.0 kHz), rectified, and integrated. The amplified and filtered nerve signal is also led to an audio monitor and through a resistance capacitance circuit (time constant 100 ms). The integrated nerve signal is digitized at 400 Hz along with the ECG signal while respiratory and arterial pressure signals are also sampled at 400 Hz (MacLab 8s). Data for analysis is selected from periods of quiet breathing in which subjects were relaxed and not talking. Microneurography was approved under HIC protocols # 8079, #0512000875, #1609018353 and is currently used under # 2000020950.

Cardiovascular variables. Recorded with a 16-channel computerized data-acquisition system at a sampling Speed of 400 Hz (ADI Instruments PowerLab 9, Castle Hill, Australia). Beat-to-beat DBP, SBP and pulse interval (PI) are determined using peak detection algorithms (44). Brachial artery BP and HR are measured with an automated sphygmomanometer (Colin Medical Instruments Corp, Komaki, Japan). Heart rate and pulse interval will be determined beat-to-beat from lead II of the EKG recording.

[figure not shown]
Visit 5 – Sympathetic Nervous System Activity (SNSA) measurement Visit – Mixed Meal Test (MMT)

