5.2.1 Primary Outcome Variables

The primary objective of this study is to determine whether sympathetic nervous system (SNS) activity in adipose tissue (WAT and BAT), muscle and brain is altered in individuals with obesity in comparison to individuals with normal weight. Simultaneous multi-organ SNS activation will be obtained with a radiotracer for norepinephrine transporters (NET) for whole-body Positron Emission Tomography (PET) imaging and microneurography (gold standard test for assessment of muscle SNS activity).

Primary outcome: SNS activity measured by [¹¹C]MRB binding in adipose tissue, muscle and brain; and sympathetic burst in muscle (measured with microneurography).

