6.1.3 Method of Assignment/Randomization

Method of Assignment/Randomization- The order of the PET scan visits 2 (PET-CT Fasting) and 3 (PET/CT-MMT) will be randomly assigned (with a 50% chance of being assigned to each visit). SNSA visits 4 (fasting) and 5 (MMT) will be also be also be randomized (with a 50% chance of being assigned to each visit).

Blinding and Procedures for Unblinding

N/A

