7.5 Data Collection

All digital data will be stored either on a secured server or on University encrypted desktops or laptops. All staff members that come into contact with the data are fully trained to the current HIPAA regulations and are informed as to the proper use of all data. Identifiable paper information is kept in locked file drawers and password protected computer files. Results are published as group data without the use of characteristics that would identify individual subjects. We quote information only by number in conference discussions, scientific reports, or publications, in order to maintain anonymity. Identifiable research data, including recruitment and screening information and code keys, are stored on a secure database located on the internal PET Center Network. The PET network is protected by a Cisco PIX firewall operated by ITS. All research data are backed up nightly to a Dell PV-136T library with 4 IBM Ultrium-TD2 tape drives using the backup software Legato Networker 7.3 from EMC. Human subjects enrolled in the study are assigned a subject-specific random identifier. Subject identifiers and the means to link the subject names and codes with the research data are stored in separate locations within the database. The software of the database limits the ability to connect the random identifier to the actual subject identification information to research team members only. Access to the database is password protected and each research team member is required to have a unique ID and password to gain access to the database. Authorized users employ their netid and authentication is performed using Yale's central authentication server. Users always access research data through the random identifier only. Direct identifiers belonging to subjects who withdraw from the study, will be stripped from the key.

The data will be stored in locked filing cabinets and on the password-protected secure database on the internal Yale University PET Center Network for at least 7 years after the close of the study, accessed only by authorized personnel. After 7 years, the data will be de-identified. Data may be kept indefinitely.

HIC 2000030749

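### Blinding is entered as N/A and no section masks readers, although MSNA burst frequency, a primary outcome, depends on selecting data and identifying bursts; score coded neurograms and lock the scores before unmasking.

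*Combined protocol and SAP*

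**What the plan says.** - **Blinding.** Section 6.1.3 carries the heading "Blinding and Procedures for Unblinding" with the single entry N/A. No other section masks the MSNA readers, the PET readers or the analysts.
- **MSNA.** Section 5.1 says "Muscle sympathetic nerve activity will be quantified by identification and measurement of sympathetic bursts in the integrated neurogram", with the result expressed as bursts per unit time. On which data are used, it says "Data for analysis is selected from periods of quiet breathing in which subjects were relaxed and not talking". The Synopsis and 6.3 repeat both statements.
- **Status.** Section 5.2.1 names "sympathetic burst in muscle (measured with microneurography") as part of the primary outcome, beside [11C]MRB binding in adipose tissue, muscle and brain.
- **PET.** Section 5.1 says "a supraclavicular ROI is first manually drawn on the CT images". Inside that outline, "the fat ROI is segmented using the CT images and an intensity window from -200 to -50 HU", and an SUV cut at 1.25 then separates BAT from WAT. Brain regions "were defined in template space and are applied to the PET images". How the deltoid region is outlined is not stated.
- **Coding.** Section 7.5 says "Users always access research data through the random identifier only".
- **Expected direction.** Section 2.1.2 (food-stimulated SNS activation) describes obesity as showing raised sympathetic activity when fasting and a blunted MSNA increment after food.

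**The concern.** Burst frequency is a count divided by time. A reader who chooses the stretch of recording and decides which deflections are bursts acts directly on both parts. If that reader knows whether the participant is lean or obese, and whether the visit was fasting or after the meal, borderline calls can drift toward the expected answer. Such drift would not average out: it would enter the group difference (primary) and the meal response (secondary objective 3) as systematic error, and neither a larger sample nor the mixed model in 6.4.1 would remove it.

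The outlining of the supraclavicular fat region raises the same question for BAT and WAT binding, in a weaker form.

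**Working it through.** **Step 1. Where judgement enters each primary measurement (section 5.1).**

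| Measurement | Step left to a reader | Step fixed by rule |
|---|---|---|
| MSNA burst frequency | Which quiet-breathing data are used; which deflections are bursts | 10-minute rest recording; 7-minute paced-breathing period at Visit 4; general quiet-breathing criterion |
| BAT and WAT binding | Supraclavicular outline on CT | HU window; SUV 1.25; MRTM2 with k2' and t* fixed |
| Brain binding | None described for region placement | Template regions |
| Deltoid binding | Not stated | Not stated |

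The same section says that beat-to-beat blood pressure and pulse interval come from peak-detection algorithms. It gives no comparable rule for bursts. That segments are chosen by hand is therefore an inference from the absence of a rule; the text does not say so.

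**Step 2. Does anything else in the plan mask the reader?** The random identifier in 7.5 sits among the confidentiality measures and is not described as concealing group or visit. Randomising visit order (6.1.3) addresses order effects and leaves open what the reader knows. Neither fills the gap.

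**Step 3. Check of the calculation against the plan's own figure.** Section 6.4.2 gives BAT DVR 1.15 (SD 0.19) lean and 0.80 (SD 0.12) obese.

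- d = (1.15 − 0.80) / √[(0.19² + 0.12²)/2] = 0.35 / √0.02525 = 2.20, as stated.
- Two-sample t-test power from the noncentral t, two-sided. Alpha is not stated in the plan; 0.05 is assumed.
- Power is 86.0% at 5 per group and 92.9% at 6 per group. Six is the smallest number reaching 90%, which matches the plan.

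This only confirms that the method behaves as the plan's does. The masking point does not depend on the sample size.

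**Step 4. Illustration of what a reader shift could do.** Assume no true difference, 20 per group (5.3.1), a two-sided 5% t-test and a systematic shift of b SD. The t-test is a simplification of the planned mixed model. The rejection probability is P(|T| > t₀.₉₇₅,₃₈), with T noncentral t on 38 degrees of freedom and noncentrality b·√(20/2) = 3.162·b.

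| b (SD) | Noncentrality | False-positive rate |
|---|---|---|
| 0 | 0 | 5.0% |
| 0.1 | 0.316 | 6.1% |
| 0.2 | 0.632 | 9.5% |
| 0.3 | 0.949 | 15.2% |

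With 18 per group after the plan's 10% loss (20 × 0.9), the rates at 0.1, 0.2 and 0.3 SD are 6.0%, 9.0% and 14.1%.

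For a paired fasting/meal comparison within one group of 20, the noncentrality is b·√20, with b now in SDs of the within-person difference. Shifts of 0.1, 0.2 and 0.3 give 7.1%, 13.6% and 24.7%. The units differ, so the two sets should not be compared line by line.

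The documents give no reader-bias size and no MSNA standard deviation. The shifts are assumed and cannot be converted to bursts per minute.

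**The case against.** **N/A may mean less than it seems.** It is a template entry under Treatment, where participants plainly cannot be masked to a meal. It does not say that readers know group or visit. Microneurography was approved under other institutional protocols, which may contain scoring procedures and are not available here. This stands as a caution: the documents show that masking is not planned in writing. They do not show how reading is done.

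**Discretion over MSNA is bounded.** There is a criterion (quiet, relaxed, not talking), respiration is recorded, the rest recording is fixed at 10 minutes, and an acceptable site must show bursts locked to the cardiac cycle. This narrows the room for choice but does not close it. No segment length or burst threshold is given, and the plan does not say whether rest, paced breathing or both supply the analysed value.

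**The hypothesis is not formally directional.** Section 4.1 speaks of dysfunction and 4.2 of alteration; direction appears only in the background. That is correct, and the point rests only on the background expectation.

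**PET is mostly rule-based.** A reader might infer that PET regions in general are hand-drawn, or that re-coding would hide the meal on every scan. The documents support neither. Manual work is described for the supraclavicular outline alone. The scan extends to the lower abdomen and, at Visit 3, follows a liquid meal of about 16 ounces, so an uncropped CT may reveal the condition. CT also shows body size, so group cannot be hidden there. For BAT, a 0.3 SD shift would be about 14% of the planning effect (0.3/2.20). Section 6.4.2 gives no planning effect for MSNA to set beside this.

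**Conclusion.** The point holds for MSNA. A primary outcome depends on data selection and burst identification, no masking is planned, and the background states the direction expected. Coded traces can be read without knowledge of group or visit at little cost, so N/A is a weaker choice than one readily available.

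It holds in reduced form for BAT and WAT, through the supraclavicular outline only. It does not apply to placement of the brain regions, and nothing can be said about the deltoid region.

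A reader might conclude that the results will be biased, or that the false-positive rate will be 9.5% to 15.2%. The documents do not support that. They show an opportunity for bias. The 6.1% to 15.2% range rests on assumed shifts of 0.1 to 0.3 SD, a 5% two-sided level that the plan does not state, and a t-test standing in for the mixed model.

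**What to change.** Replace the N/A entry with a short masked-reading procedure.

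**MSNA**
1. After acquisition, existing staff export each neurogram under a fresh code that hides BMI group and fasting/meal visit. Forty participants with two MSNA visits each give at most 80 planned recordings (40 × 2).
2. The existing analyst selects segments and scores bursts on the coded files by one rule written beforehand. The rule states which recording period is used, the segment length and what counts as a burst.
3. Scores are locked before the codes are linked.
4. Section 3.2.1 assigns the recordings to one or other of two microneurographers. Where practical, the one who did not record a session scores it.

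**PET**
- Draw the supraclavicular outline on CT images cropped to the neck and shoulder region and coded for visit, and lock it before PET values are viewed.
- State that masking to body size is not achievable here. Brain regions need no change.

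**Cost.** A small re-coding and cropping step by existing staff. No visit, participant procedure or sample size changes. Masking will be incomplete if a reader remembers a session or infers the condition from accompanying signals such as heart rate; the plan should acknowledge this.

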High Carbohydrate Mixed meal test (MMT): Two weeks after visit 2, participants will come to the PET Center after a 10-hour overnight fast. A nurse will insert an intravenous (IV) catheter and subjects will ingest a liquid meal (65% CHO, 20% fat, and 15% protein, equal to 40% of daily energy expenditure, per ~16 ounces) to be prepared by the Metabolic Kitchen located at the HRU. Blood samples will be collected at -10, 0, 15, 30, 60, 90, and 120 min for measurement of glucose, insulin and C-peptide concentrations ⁷. Plasma samples will be drawn at baseline and throughout the MMT for measurement of additional hormones (such as leptin, ghrelin, thyroid hormones, and catecholamines) and free fatty acids (FFA) levels. Insulin and glucose will be used to calculate indexes of insulin sensitivity ⁷⁻⁹. Hormones, glucose and FFA will be correlated with PET measurements of brown fat at baseline and during the MMT. Approximately 60 mL of blood will be drawn at this visit.

HIC 2000030749

Participants will undergo whole body [¹¹C]MRB PET scan as described in visit 3. After the MMT, PET data will be acquired dynamically for 120 min using the Siemens mCT-X whole-body PET/CT scanner after an intravenous bolus dose of MRB (~20mCi).

The order of the PET scan visits 2 and 3 will be randomized.

PET and MSNA visits do not need to occur in sequence, i.e. PET scans can occur before or after the MSNA.

Measurement of Energy Intake: Hunger and fullness will be determined immediately before, during and after the PET scans with Visual Analog Scales (VAS).

Visit 4 – Sympathetic Nervous System Activity (SNSA) measurement Visit - Fasting

Two weeks after visit 3, participants will be asked to return for a separated visit for measurements of SNS activity at rest and fasting. This visit will be performed at the Pierce Laboratory ([name] laboratory). The participants will come in the morning (~9am) and will be asked to fast for 10-hour and to maintain their regular exercise routine. The following measurements will be obtained: MSNA, heart rate (HR), blood pressure (BP), electrocardiogram (EKG), and heart rate variability. The proposed procedures will be performed at fasting (baseline). Participants will be asked to maintain their regular exercise routine.

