Two weeks after visit 4, participants will be asked to return for a separated visit for measurements of SNS activity at rest and after intake of liquid meal. Participants will undergo similar procedures described on visit 4. However, MSNA will be obtained after MMT. The participants will come in the morning (~9am) and will be asked to fast for 10-hour and to maintain their regular exercise routine. A nurse will insert an intravenous (IV) catheter and subjects will ingest a liquid meal (65% CHO, 20% fat, and 15% protein, equal to 40% of daily energy expenditure, per ~16 ounces) to be prepared by the Metabolic Kitchen. Measurements of HR, BP, and EKG (beat-to-beat) will be obtained during the procedure. An intravenous catheter will be inserted into a forearm vein for blood sampling. Following the instrumentation period, resting HR, pulse interval (PI), BP, and MSNA will be recorded for 10 minutes. Following these measurements, plasma will be taken for measurements of insulin, glucose, free fatty acids, norepinephrine, and epinephrine levels. Approximately 40 mL of blood will be drawn at this visit.

HIC 2000030749

Participants will be asked to maintain their regular exercise routine. The order of SNSA Fasting and MMT visits (visits 4 and 5) will be randomized. All study visits will be conducted within an 8-week period (including the two PET and SNSA scans).

Schematic figure of the visits and procedures to be done. The order of the PET scans will be randomized.

Abbreviations: BP=blood pressure, EKG=electrocardiogram, HR=heart rate, MSNA=Muscle sympathetic nerve activity, SNSA=Sympathetic Nervous System Activity

Method of Assignment/Randomization- The order of the PET scan visits 2 (PET-CT Fasting) and 3 (PET/CT-MMT) will be randomly assigned (with a 50% chance of being assigned to each visit). SNSA visits 4 (fasting) and 5 (MMT) will be also be also be randomized (with a 50% chance of being assigned to each visit).

PET and MSNA visits do not need to occur in sequence, i.e. PET scans can occur before or after the MSNA.

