6.4 Statistical Method

6.4.1 Statistical Design

Primary endpoints: Group differences in 1) [¹¹C]MRB-binding in brown adipose tissue (BAT), white adipose tissue (WAT), skeletal muscle, and norepinephrine-rich brain regions (hypothalamus and thalamus); and 2) microneurography (muscle sympathetic nerve activity (MSNA)). Correlations between NET in the brain and peripheral NET and MSNA.

Secondary endpoints: Plasma hormone levels, heart rate, blood pressure, electrocardiogram (beat-to-beat)..

Statistical Analysis: Before statistical testing, all continuous variables will be tested for normality of distribution. Summary statistics will be computed. For between-group comparisons of patient characteristics, two sample t-test or Mann-Whitney U test will be used for continuous variables, and Fisher's exact test for categorical variables. Comparisons of repeatedly measured MSNA will be made using the mixed model analysis. Fixed factors include group and sex and their interactions. Linear contrasts comparing differences between groups or different time points within a group will be estimated.

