6.4.2 Sample Size Considerations

Statistical Considerations: sample sizes of 6 per group (normal BMI x obesity, and women x men) will achieve 90% power to detect a between-group difference. To account for up to 10% missing data due to drop out or poor-quality data, we will need to enroll a total of 40 subjects (10 per group) for this study.

Fasting: A Power analysis was performed based on previous study published from our group in lean and obese female individuals: (lean 1.15 ± 0.19 vs obese 0.80 ± 0.12 BAT DVR, $p = 0.004$; two-sided independent sample t-test)². In our previous cross-sectional comparison,

HIC 2000030749

using the mean and standard deviations between lean and obese individuals, we expect an effect size of $d=2.20$ and with a power of 0.90, to account for possible smaller differences in males, we need 6 individuals per group. For reference, $d=2.20$ and 0.80 power would be 5 per group.

MMT: Postprandial whole-body energy expenditure per fat free mass (FFM) differences were shown for low-BAT (32 ± 2 kcal/day/kg FFM) and high-BAT (37 ± 2 kcal/day/kg FFM)⁴⁵. Based on these data, we can calculate an effect size of $d=2.50$. With a power of 0.80 required, we will need 8 individuals (4 per group) determine EE differences between low- and high-BAT individuals. Increasing the power to 0.95 will increase the number of individuals to 12 (6 per group). Due to the technical challenges of performing microneurography on multiple occasions in obese women, we overestimate and account for $\sim 10\%$ failure rate, so we will recruit 10 subjects per group.

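### At Visit 5 the post-meal MSNA recording is tied to the end of instrumentation, and the time from meal to recording is neither fixed nor logged

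*Combined protocol and SAP*

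**What the plan says.** Section 5.1 defines Visit 5 largely by reference to the fasting visit: "Participants will undergo similar procedures described on visit 4". It then adds the one distinguishing instruction, "However, MSNA will be obtained after MMT". In the order written, an IV line is placed, the liquid meal is drunk, and then: "Following the instrumentation period, resting HR, pulse interval (PI), BP, and MSNA will be recorded for 10 minutes". The Synopsis and Section 6.3 repeat this account. The schedule tables (Synopsis, Sections 6.2, 6.3.1 and 6.3.5) list the meal and MSNA for Visit 5 without any times.

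Instrumentation includes finding the nerve: "The time required to focus the electrode on the nerve averages about 30 min and will not exceed 60 min". The Visit 4 procedure that Visit 5 inherits also says "The experiment will begin with a 60-minute control period", but Visit 5 does not place that period before or after the meal.

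The PET meal visit (Visit 3) is handled differently: "Blood samples will be collected at -10, 0, 15, 30, 60, 90, and 120 min for measurement of glucose, insulin and C-peptide concentrations". Visit 5 has no such grid.

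On the analysis side, Section 6.4.1 lists among the primary endpoints group differences in "microneurography (muscle sympathetic nerve activity (MSNA)). Correlations between NET in the brain and peripheral NET and MSNA", without naming a visit. The before-and-after-meal comparison is secondary objective 3 (Section 4.3). The mixed model for MSNA (Sections 6.4.1 and 6.5.1) names group, sex and their interaction. It mentions contrasts between time points but does not define them. Section 6.5.9, on covariates, is marked not applicable.

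**The concern.** The background section expects a sympathetic response to the meal, and expects it to be blunted in obesity. A response that rises and falls after eating can be compared between people only at a common time after eating. Here the recording is triggered by completion of instrumentation, an event whose timing varies from person to person, and not by the meal.

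Two things follow. Variation in delay that is unrelated to group adds noise to the post-meal value and to the change from the fasting visit. If average delay differed between lean and obese participants, part of the group contrast would be a contrast of clock times, which could imitate, hide or exaggerate blunting. Randomising the order of Visits 4 and 5 does not protect against this: obesity is not randomised, and the delay arises only at the meal visit. If the interval is not logged during the session, it cannot be recovered at analysis.

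**Working it through.** **The plan's own figures.** The plan gives no figure for meal-to-recording time, post-meal MSNA slope, MSNA standard deviation or search time by group. Its only calculations are the sample sizes in Section 6.4.2. With a two-sided t-test at 5% (alpha is not stated, so this is assumed):
- Fasting: d = (1.15 − 0.80)/√((0.19² + 0.12²)/2) = 2.20, which needs 5.51, so 6 per group, at 90% power.
- Meal: d = (37 − 32)/2 = 2.50, which needs 3.76, so 4 per group, at 80%, and 5.34, so 6 per group, at 95%.

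These reproduce. They concern brown-fat DVR and energy expenditure, not MSNA, so they neither support nor weaken this point.

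**Possible spread in timing.**
- Electrode placed after the meal: search time runs up to 60 min with a mean of about 30 min, so the search alone can separate two participants by up to about 60 min. Two 10-minute recordings that start more than 10 min apart do not overlap.
- The 60-minute control period, if it also follows the meal, moves everyone by the same amount. It adds delay but no spread.
- Electrode placed before the meal: the search adds no spread, but the interval from drinking to recording is still unspecified.

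For scale, 60 min is the distance from the 30-minute to the 90-minute sample on the Visit 3 grid.

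**Illustration of consequences.** Everything here is assumed: MSNA changes linearly after the meal by 0.25 to 1.0 between-person SD per hour, and mean delay differs between groups by 10 to 30 min.

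Spurious group difference (SD) = slope per hour × difference in delay (min)/60. The rejection rates are for a two-sided 5% t-test when there is no true group difference.

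| Slope (SD/h) | Delay difference (min) | Spurious difference (SD) | Rejection, 20 per group | Rejection, 10 per group |
|---|---|---|---|---|
| 0.25 | 10 | 0.04 | 5.2% | 5.1% |
| 0.50 | 20 | 0.17 | 8.1% | 6.4% |
| 1.00 | 30 | 0.50 | 33.8% | 18.5% |

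For noise alone, take a delay spread evenly over 0 to 60 min in both groups. Its variance is 1/12 h², so the SD is multiplied by √(1 + slope²/12): 1.003, 1.010 and 1.041 for slopes of 0.25, 0.5 and 1.0. The noise is therefore small under these assumptions. The bias, if there is one, ranges from negligible to serious.

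**The case against.** The strongest objection is that the written order in Section 5.1 is not a dependable chronology. The Visit 5 text inserts the IV catheter twice, once before and once after the meal, and from the monitoring sentence onward it nearly repeats the Visit 4 text. A search after the meal is the natural reading but is not stated. If the electrode goes in first, the 60-minute spread disappears. This stands, and it is why the point is made conditionally. It does not close the gap, because under either order no interval is set.

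Second, a pre-meal recording in the same session may already be intended. Visit 5 is introduced as measuring activity both at rest and after the meal, the analysis refers to repeated MSNA measurements, and about 40 mL of blood is drawn against 20 mL at Visit 4. None of this is decisive, since Visit 4 can supply the fasting value. It does mean that the request should be to specify the sequence, not to redesign the visit.

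Third, a reader might infer that the sponsor expects longer searches in obese participants, so that timing is likely to differ by group. Section 6.4.2 does begin a sentence with "Due to the technical challenges of performing microneurography on multiple occasions in obese women", but that sentence goes on to allow for a failure rate of about 10%. It concerns failed recordings in obese women. It says nothing about search duration, and nothing about obese men, who are half of the obese group. A failed search gives a missing value, not a late one. The search is also capped, and ultrasound guidance is allowed. The documents do not support that inference.

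**Conclusion.** The plan leaves the post-meal time of the Visit 5 MSNA recording unfixed and unlogged, and the model has no term for it. Followed as written, it can compare participants at different times after the meal. The spread could reach about an hour if the electrode is placed after the meal, and is unknown if it is placed before.

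This affects post-meal MSNA and the fasting-to-meal change under secondary objective 3. Fasting MSNA at Visit 4 is untouched, and no sample size figure changes.

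The point does not extend to a claim that the lean-obese contrast is biased, or that a blunted response would be an artefact. That would need a group difference in delay and a known post-meal slope, and the documents give neither. The range of 0.04 to 0.50 SD above rests wholly on assumed values, and the direction of any bias is unknown. It is worth acting on because the remedy is cheap and unlogged times are lost for good.

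**What to change.** In the Visit 5 text of the Synopsis and Sections 5.1 and 6.3:
1. State the order of electrode placement, control period and meal, preferably with the electrode placed first.
2. Record MSNA for everyone in one fixed window of minutes after ingestion, with a stated tolerance, for example at a time on the Visit 3 sampling grid. If the electrode is to follow the meal, the window must come late enough to accommodate a 60-minute search.
3. Log the actual minutes from meal to start of recording.

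In Sections 6.4.1, 6.5.1 and 6.5.9: define the MSNA time points, include the logged interval in the mixed model for the meal-visit recording, at least as a sensitivity analysis, and say how recordings outside the window are handled. A pre-meal recording in the same session is optional.

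**Cost.** Placing the electrode first means longer electrode time and some risk of losing the site while the participant drinks. Logging costs almost nothing. The covariate costs a little precision, and more if delay turns out to be related to group, and it relies on an assumed shape for the post-meal response. A fixed window is therefore the main protection and adjustment the back-up.
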